**FORM: Application for Human Research**

NUMBER	FORM DATE	PAGE
F200	02/2014	2 of 39

**FORM: Application for Human Research**

NUMBER	FORM DATE	PAGE
F200	02/2014	3 of 39

**FORM: Application for Human Research**

NUMBER	FORM DATE	PAGE
F200	02/2014	4 of 39

**SECTION 2: GENERAL INFORMATION**

1. Not including this project submission, how many:

- Human Research studies is the PI involved in as key personnel?   
3 to be IRB approved for opening, key personnel on 5 studies
- Active subjects are there in the PI's open Human Research study/ies?   
15 active subjects at Harvard of 155 enrolled or completed; studies to be transferred to a site PI upon [name] transfer
- Investigators are involved on the PI's open Human Research studies?   
0
- Research coordinators are involved on the PI's open Human Research studies?   
3

2. What is the expected length of this project?   
3 years

3. Retention of study materials before, during, and after completion of the project:

- Where will the original signed consent and PHI Authorization documents be stored (building name and room)?   
AHSC 7327A
- How long will the data/consents be kept after conclusion of the project?   
 6 years  
 Other: Indefinitely

4. If the Human Research project is funded, identify all sponsoring entity/ies:   
Department of Defense (DoD)

5. If funding support is from a federal agency (such as a training grant, infrastructure grant, salary support, project grant, etc.), list federal agency and grant number   
Awaiting notice of award;  
Proposal ID PT130230

6. Total funding amount **OR** per subject amount:   
To be determined; awaiting award

7. The Principal Investigator hereby affirms that ALL individuals who meet the definition of "investigator" for this project in the current "Policy on Investigator Conflict of Interest in Research" have completed the mandatory Conflict of Interest training (<http://orcr.arizona.edu/coi/training>) and Disclosure of Significant Financial Interests (<https://uavpr.arizona.edu/COI/>).   
 Yes

8. Will this project be registered on ClinicalTrials.gov because ...?   
 Yes  No

- the local PI is the sponsor of the clinical trial (including NIH-funded clinical trials where the local PI is the funding recipient OR IND holder);  
**OR**
- The PI has been designated by a sponsor, contractor, grantee, or awardee to register the clinical trial to [ClinicalTrials.gov](http://ClinicalTrials.gov), as the [Responsible Party](#) (responsible for conducting the trial, and has sufficient data rights)

**FORM: Application for Human Research**

NUMBER	FORM DATE	PAGE
F200	02/2014	5 of 39

If yes, please check the appropriate box:

[ClinicalTrials.gov](#) "NCT" number for this trial (define): NCT02374918

Registration pending

Clinical trial does not require registration (click above to see what studies qualify)

**SECTION 3. PROJECT NARRATIVE****1) Background**

Mild traumatic brain injury (mTBI) has been described as the “signature injury” of the current conflicts in Iraq and Afghanistan (Fear et al., 2008). Improvised explosive devices (IEDs) are often the weapons of choice by insurgents in the current conflicts. With the advances in body armor, many casualties of an IED who would have been killed in earlier conflicts now have a high probability of surviving (Okie, 2005). The detonation of an IED produces a number of blast-related effects on the body, the severity of which is usually dependent on the proximity to the point of the explosion. Soldiers who are not directly killed by an IED explosion may still suffer blast related injuries from the overpressure wave, from flying debris, or from being propelled against the ground or a fixed object. Any of these can produce a head injury. Moderate and severe head injuries are typically obvious due to the level of external damage and debilitation, and usually result in rapid medical evacuation to a medical treatment facility. Less obvious injuries may also occur when a Soldier sustains a head injury but fails to lose consciousness and merely appears “stunned” or “dazed” to other unit members or may regain consciousness within a few seconds to minutes after the injury. In such cases, a mild traumatic brain injury (mTBI) or “concussion” is likely to have occurred, but may not be diagnosed until much later, if at all. Hoge and colleagues recently reported that 4.9% of a large sample of U.S. Army Soldiers returning from wartime deployment in Iraq endorsed having an injury with a loss of consciousness, while an additional 10.3% reported an injury with some form of altered mental status such as being “dazed, confused, or seeing stars” (Hoge et al., 2008). Typically, most mTBI patients show a resolution of their symptoms within a matter of days or weeks (McCrea et al., 2003), with nearly complete return to baseline functioning within 3 months of their injury. However, a small proportion of mTBI patients will continue to have chronic symptom complaints (Ryan & Warden, 2003), a condition which has been described as the post-concussive syndrome (PCS).

Patients with post-concussion syndrome have been shown to have deficits on tests of short term memory, divided attention, multi-tasking, information processing speed, and reaction time (Bigler, 2008; Pare, Rabin, Fogel, & Pepin, 2009), as well as alteration in mood and emotional functioning (Bigler, 2008). Many patients have other vague complaints including fatigue, dizziness, irritability, sleep disturbances, and chronic headaches (Bigler, 2008; Haboubi, Long, Koshy, & Ward, 2001; Packard, 2008). Furthermore, sleep disruption of one of the most common complaints in patients suffering from traumatic brain injuries (Baumann, Werth, Stocker, Ludwig, & Bassetti, 2007; Castriotta et al., 2007; Makley et al., 2008; Parcell, Ponsford, Redman, & Rajaratnam, 2008; Rao et al., 2008; Verma, Anand, & Verma, 2007; Williams, Lazic, & Ogilvie, 2008), with as many as 40 to

**FORM: Application for Human Research**

NUMBER	FORM DATE	PAGE
F200	02/2014	6 of 39

65% of patients with mTBI complaining of insomnia (Beatar, Guilmette, & Sparadeo, 1996; Dikmen, McLean, & Temkin, 1986). Sleep problems in these patients are associated with poorer outcome (Franckeviciute, Varzaityte, & Kimtys, 2008), while resolution of the sleep disturbance is associated with improvement in cognitive functioning (Makley et al., 2009). A recent study demonstrated that sleep disturbances, including reduced sleep efficiency, longer sleep onset latency and shorter REM onset latency, were more persistent in mTBI patients for nearly three years after the injury (Williams et al., 2008), and others have found similar long lasting sleep disruption in these patients (Schreiber et al., 2008). Additionally, sleep complaints have been correlated with increased likelihood of mood disturbance and headaches in post-concussive patients (Chaput, Giguere, Chauny, Denis, & Lavigne, 2009). It has been suggested that mTBI might produce alterations of the normal circadian rhythm, leading to delayed sleep phase syndrome and irregular sleep-wake patterns (Ayalon, Borodkin, Dishon, Kanety, & Dagan, 2007). Of mTBI patients with complaints of insomnia, 36% were recently found to have circadian rhythm sleep disorders that emerged following the brain injury (Ayalon et al., 2007). Moreover, the important relationship between sleep and recovery in patients with brain injuries was highlighted in a recent study that showed that sleep efficiency was correlated with the resolution of post-traumatic amnesia in patients with closed head injuries (Makley et al., 2009). Thus, there is little doubt that mTBI is associated with significant disruption of normal sleep patterns and that poorer sleep is associated with poorer recovery, while improvement in sleep problems is associated with improvement in cognitive functioning.

Despite recent evidence of the correlation between sleep quality and recovery from traumatic brain injury (Makley et al., 2009), and the well-established role of sleep in neural plasticity (Aton et al., 2009; Stickgold & Walker, 2007; Walker, 2009; Walker & Stickgold, 2006) and neurogenesis (Hairston et al., 2005; Meerlo, Mistlberger, Jacobs, Heller, & McGinty, 2009), there have been virtually no direct studies of the causal effects of sleep on recovery following mTBI. However, it is quite likely that sleep plays a critical role in recovery following brain injury. First, sleep facilitates learning of new skills and information and leads to functional reorganization of the brain (Orban et al., 2006). It has long been known that sleep following learning enhances subsequent retrieval and performance (Diekelmann, Wilhelm, & Born, 2009; Ellenbogen, Hulbert, Jiang, & Stickgold, 2009; Walker & Stickgold, 2006), and recent studies have shown that sleep is a critical factor in synaptic strengthening following learning (Aton et al., 2009) and that hippocampal-cortical reorganization occurs during sleep (Yordanova, Kolev, Wagner, & Verleger, 2009). New evidence also suggests that sleep quality before learning is also critical to hippocampal encoding, such that even a small disruption in sleep can affect declarative learning the subsequent day (Van Der Werf et al., 2009). Thus, sleep and new learning appear inextricably linked. Second, the quantity and quality of sleep affects a variety of hormonal systems that may influence brain function and repair, and sleep may also be important in reducing oxidative damage to neurons and provide an opportunity for neural resynchronization (Schulze, 2004). Sleep is also hypothesized to be critical to neural development (Marks, Shaffery, Oksenbergs, Speciale, & Roffwarg, 1995), functioning, repair, and plasticity (Frank, 2006; Frank, Jha, & Coleman, 2006; Gally & Edelman, 2004). This plasticity is reflected in the growth of new synapses in response to learning (C. Smith, 1996). Moreover, some recent evidence suggests that sleep may be critical in the neurogenesis (Meerlo et al., 2009) and proliferation (Tung, Takase, Fornal, & Jacobs, 2005) of neurons in the hippocampus, a brain structure that is critical to the formation of new memories (Guzman-Marin, Bashir, Suntsova, Szynusiak, & McGinty, 2007;

**FORM: Application for Human Research**

NUMBER	FORM DATE	PAGE
F200	02/2014	7 of 39

Guzman-Marin et al., 2008; Hairston et al., 2005; Mueller et al., 2008). Prolonged sleep restriction or sleep deprivation appears to have cumulative effects that severely impair hippocampal cell neurogenesis, proliferation, and survival (Meerlo et al., 2009). Of relevance to the presently proposed study, a recent discovery suggests that melatonin, a hormone that is closely linked to light-dark cycles and circadian sleep patterns, is the only known exogenously applicable chemical associated with increased cell survival of newly formed neurons in the rat hippocampus (Ramirez-Rodriguez, Klempin, Babu, Benitez-King, & Kempermann, 2009). While no studies have directly examined the effects of sleep on recovery from mTBI, there is evidence that sleep is essential in restoring motor learning following a cerebrovascular accident (C. Siengsukon & L. A. Boyd, 2009). For example, patients recovering from stroke showed significant improvement in motor learning following sleep compared to those without sleep (C. F. Siengsukon & L. A. Boyd, 2009b). Moreover, this enhancement of learning was much stronger in the stroke rehabilitation group than in a healthy control group, suggesting that sleep may play an important role in recovery from brain injury. Other studies have shown that the quality and quantity of sleep following stroke is correlated with recovery of cognitive functions (Siccoli, Rolli-Baumeler, Achermann, & Bassetti, 2008). Emerging perspectives on rehabilitation are beginning to focus on the importance of sleep in rehabilitation of patients following brain injuries such as stroke (C. F. Siengsukon & L. A. Boyd, 2009a). Because mTBI disrupts normal neural functioning and may even lead to cell death, rehabilitative efforts may be most effective if they facilitate these processes, all of which are protected or enhanced by adequate sleep. Without adequate sleep, normal brain repair processes are likely to be hampered. Therefore, research efforts aimed at understanding the effects of sleep and circadian misalignment on the recovery process are necessary.

A particularly promising non-pharmacologic approach that shows potential in improving/modifying abnormalities of the circadian rhythm and sleep-wake schedule is bright light therapy, particularly within the blue-wavelength spectrum (Brainard et al., 2008; Phipps-Nelson, Redman, Schlangen, & Rajaratnam, 2009; Revell & Skene, 2007; M. R. Smith, Revell, & Eastman, 2008), which involves the selective application of bright light pulses at critical points in the circadian cycle (Brainard & Hanifin, 2005; Geuze et al., 2008; Skene, Lockley, Thapan, & Arendt, 1999). The crucial effect of light on the entrainment of the circadian rhythm of sleep and wakefulness is well documented (Czeisler & Gooley, 2007; Lockley, Brainard, & Czeisler, 2003; Roenneberg & Merrow, 2007; M. R. Smith, Cullinan, & Eastman, 2008), and bright light therapy has long been recognized as an extremely effective treatment for some types of neurobiologically based mood disorders, such as Seasonal Affective Disorder (Anderson, Glod, Dai, Cao, & Lockley, 2009). Due to its mood altering effects, bright light therapy is also being explored for its effects on a variety of psychiatric conditions (Prasko, 2008; Terman, 2007).

A recent discovery has documented that there are photoreceptive ganglion cells in the retina (Dacey et al., 2005). These receptors do not appear to be involved in visual sensation, but instead have special pigmented cells that are responsive to the blue wavelengths of light, which are believed to be primarily involved in circadian regulation (Hanifin & Brainard, 2007). These melanopsin receptors are involved in light transduction and may have direct effects on several neurotransmitter and neuroendocrine systems, including serotonin (Ljubicic, Stipcevic, Pivac, Jakovljevic, & Muck-Seler, 2007) and melatonin (Brainard et al., 2001; Revell & Skene, 2007). The blue wavelengths of light, in particular, are believed to suppress melatonin (Brainard et al., 2008; Gammack, 2008;

**FORM: Application for Human Research**

NUMBER	FORM DATE	PAGE
F200	02/2014	8 of 39

Lockley & Gooley, 2006; Revell & Skene, 2007), a naturally produced hormone that is believed to be one of the primary regulators of daily rhythms, including sleep and wakefulness (Lewy, Emens, Jackman, & Yuhas, 2006; Revell & Eastman, 2005). For example, administration of a sustained pulse of blue-enriched bright light in the early morning hours before the circadian temperature nadir suppresses melatonin and reduces the circadian drive for sleep, leading to greater overnight alertness (Lockley et al., 2006; Santhi, Aeschbach, Horowitz, & Czeisler, 2008). Morning bright light also phase advances the normal circadian rhythm, thereby reducing sleep onset insomnia (Lack, Gradisar, Van Someren, Wright, & Lushington, 2008; Lack & Wright, 2007; Skene, 2003). Given that the melanopsin receptors appear to be primarily responsive to blue wavelength light (Revell & Skene, 2007), and that similar melatonin suppressing effects can be produced with significantly lower light intensities in the blue-wavelengths, numerous studies have now begun to focus on using this wavelength for improving daytime alertness, subjective sleep quality (Viola, James, Schlangen, & Dijk, 2008), and phase advancing individuals with delayed sleep phase disorders (Lockley et al., 2003; M. R. Smith, Revell et al., 2008).

Presently, no published studies have examined the effects of bright or blue-enriched light therapy on outcome in mTBI patients. For the proposed investigation, we hypothesize that blue-wavelength light therapy may be helpful in improving the sleep of patients with a recent history of mTBI and may also have other mood elevating effects (Anderson et al., 2009; Glickman, Byrne, Pineda, Hauck, & Brainard, 2006), both of which should promote positive treatment outcome in these individuals. Based on recent evidence that some wavelengths may provide greater suppression of melatonin than others (Glickman et al., 2006; Herljevic, Middleton, Thapan, & Skene, 2005; Skene, 2003; M. R. Smith, Revell et al., 2008; Thapan, Arendt, & Skene, 2001), we propose to use a commercially available device with wavelengths peaking within the blue spectrum (i.e., 467), which has shown documented success in treating seasonal affective disorder (Skene, 2003) and suppressing melatonin (Fucci et al., 2005).

Interestingly, preliminary data from our own laboratory examining the effects of a 10 minute pulse of blue-wavelength light (469 nm), using the goLITE BLU device proposed for the present study, demonstrates significant increases in brain regions involved in emotional control, alertness, and self-awareness, including the lateral prefrontal cortex, thalamus, and posterior cingulate gyrus during a conflict monitoring task (see figure).

This same cognitive task will be used as part of the proposed study during fMRI scanning. We propose that direct intervention to improve the sleep difficulties in mTBI via blue light therapy may lead to entrainment of the circadian rhythm, improved sleep, and enhancement of daytime alertness. These improvements are predicted to lead to improved emotional regulation, neurocognitive performance, and accelerated improvement in symptoms among patients with mTBI.

The primary aims of the proposed study are to examine the effectiveness of a six-week course of morning blue light therapy (MBLT) on objective and subjective measures of sleep, emotional functioning, mood, psychiatric symptom expression, and neuropsychological assessment using the most current version of the Automated Neuropsychological Assessment Metric (ANAM4) TBI battery. In addition, changes in behavioral functioning produced by MBLT will also be correlated with changes in Blood Oxygen Level Dependent (BOLD) functional magnetic resonance imaging (fMRI) during an executive control task, a virtual reality water-maze task that assesses hippocampal memory function, and a working memory n-back task. These tasks have been used extensively in our

**FORM: Application for Human Research**

NUMBER	FORM DATE	PAGE
F200	02/2014	9 of 39

laboratory and provide excellent resolution for evaluating functional changes within the target regions of the anterior cingulate gyrus, hippocampus, and prefrontal cortex. Furthermore, the proposed project will directly assess sleep functioning using actigraphy and correlate these changes in sleep with pre-to post-treatment changes in neurocognitive performance and symptom presentation, as well as functional activity changes.

Briefly, individuals who have experienced a mTBI, with or without loss of consciousness, as verified by a medical report, and who complain of sleep disturbance, will undergo an initial psychological assessment, and will be then fitted with an actigraph to wear for the duration of the study in order to measure baseline sleep as well as any changes in sleep patterns. Individuals will then return to complete two comprehensive neurobehavioral assessment and neuroimaging sessions (functional MRI, structural MRI/diffusion tensor imaging; DTI) separated by 6 weeks. During the intervening 6 weeks, participants will be randomly assigned to receive 30 minutes of morning blue light therapy (MBLT) or a sham placebo amber light treatment (SPLT) daily. Sleep quality and quantity will be measured via continuous wrist actigraphy monitors and self-report inventories.

For interested subjects participating in the last phase of recruitment, we will continue collecting wrist actigraphy and self-report data for an additional 6 weeks after completion of the baseline period and light therapy as an optional part of the study. It is hypothesized that MBLT will improve sleep quality and quantity relative to SPLT, and these improvements will be associated with changes in brain function, brain structure, and reduced post-concussion symptom severity at follow-up assessment.

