### **Personality and Psychodiagnostic Assessment**

At the Baseline and Post-Treatment sessions, further assessment of psychopathology will be made via administration of the Beck Depression Inventory (BDI-II); the patient health questionnaire (PHQ); Rivermead Post-Concussion Symptoms Questionnaire (RPCSQ), Buss Perry Aggression Questionnaire (BPAQ), and Spielberger State-Trait Anxiety Inventory (STAI). Risk-taking propensity will be assessed with the Evaluation of Risks Scale (EVAR) and Invincibility Beliefs Index (IBI). Participants will also complete basic questionnaires regarding sleep history, caffeine use, Morningness-Eveningness traits (MEQ), Stanford Sleepiness Scale (SSS), Pittsburgh Sleep Quality Index (PSQI), the Epworth Sleepiness Scale (ESS), the Satisfaction with Life Scale (SWLS), and the Functional Outcome of Sleep Questionnaire (FOSQ)(Weaver et al., 1997). These measures of sleep parameters and mood state will permit comparison of the effects between treatment with MBLT and SPLT on mood and sleep (OBJECTIVE 1) and will be correlated with other measures of neurocognition and neuroimaging (OBJECTIVE 3).

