**I. BIOSTATISTICAL ANALYSIS**

Several global outcomes and their interpretations include:

- 1) “If the effects of MBLT versus SPLT are not different and improvement is observed in both groups”—this would suggest that nonspecific effects (practice, maturation, recovery) occurred but were unrelated to the MBLT treatment. Thus there is no specific benefit to the use of MBLT versus placebo. Based on such an outcome, there would be no recommendation for the use of MBLT for treatment of post-concussive symptoms. Secondary analyses correlating cognitive/symptom improvement with changes in brain structure and function may identify new avenues of research and would still contribute valuable knowledge regarding these relationships.
- 2) “If effects of MBLT versus SPLT are not different and no significant improvement is observed in either group”—this finding is less likely, as continued improvement between the two sessions would be expected due to gradual recovery during the first year and due to practice effects associated with repeated assessment. While such a finding would clearly suggest that there is no specific benefit to the use of MBLT versus placebo, it would raise suspicion that the assessments were invalid or insensitive.
- 3) “If MBLT is better than SPLT”—this is the hypothesized effect. This would support the hypothesis that MBLT is beneficial in the treatment of post-concussive symptoms relative to placebo. Regression analysis between the change in symptoms/neurocognitive function and measures of sleep and mood would identify whether this was due to sleep related changes or whether the changes were due to the mood altering effects of MBLT, or both. Similarly, changes in one condition and not the other will also be examined for their relationship to

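### Sleep change is related to symptom and mood scores that may themselves contain sleep and fatigue content, and no analysis without that content is planned.

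*Combined protocol and SAP*

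**What the plan says.** The study overview at the end of Section 3, 1) Background predicts better sleep on morning blue light (MBLT) than on sham amber light (SPLT), and that "these improvements will be associated with changes in brain function, brain structure, and reduced post-concussion symptom severity at follow-up assessment". On measurement it says: "Sleep quality and quantity will be measured via continuous wrist actigraphy monitors and self-report inventories". The correlation that it spells out uses the objective measure: the project will "directly assess sleep functioning using actigraphy and correlate these changes in sleep with pre-to post-treatment changes in neurocognitive performance and symptom presentation".

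Under I. Biostatistical Analysis, the third listed outcome (MBLT better than SPLT) adds an explanatory step: "Regression analysis between the change in symptoms/neurocognitive function and measures of sleep and mood would identify whether this was due to sleep related changes", or to the effect of light on mood, or to both.

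On what counts as a post-concussion complaint, the Background says: "Many patients have other vague complaints including fatigue, dizziness, irritability, sleep disturbances, and chronic headaches".

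Under 7) Procedures, Personality and Psychodiagnostic Assessment names the RPCSQ, BDI-II and PHQ, and on the sleep side the SSS, PSQI, ESS and FOSQ. Neurocognitive Assessment describes the ANAM4 battery, which has a sleepiness scale, a 21-symptom checklist and a seven-category mood scale that includes Fatigue and Vigor. The documents do not say whether totals or subscores are analysed. They plan no score without sleep and fatigue content, and no sensitivity analysis on this point.

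**The concern.** If a symptom score counts poor sleep or tiredness as symptoms, a participant whose only change is better sleep also improves on the symptom score. Across participants, the two changes then correlate even if headache, dizziness, irritability and memory complaints have not moved. Such a correlation would read as support for the mechanistic idea behind the trial, that better sleep goes with recovery from mTBI, when it may show only that sleep complaints follow sleep.

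The regression under the third outcome has a related problem. It is meant to separate sleep from mood, but a mood score with a fatigue component carries part of what the sleep measures carry. Some of a sleep effect can then be credited to mood, or the reverse.

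**Working it through.** **The plan's own figure.** There is none. The documents give no correlation, significance level, power or effect size for this analysis. What follows is an illustration under stated assumptions.

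**Inputs from the documents.** 30 complete datasets (5) Study Population); 21 symptoms in the ANAM checklist and 7 mood categories, two of them Fatigue and Vigor (Neurocognitive Assessment, item 1).

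**Assumptions.** Two-sided 5% test. Unit-variance change scores, signed so that improvement is positive. Of *k* items, *s* overlap with sleep. Each overlapping item correlates *a* = 0.3 to 0.7 with the sleep measure, and overlapping items correlate 0.5 with each other. The other items correlate ρ = 0.1 to 0.5 among themselves, and are unrelated both to sleep and to the overlapping items.

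**Formulas.**
- Var(total) = s + 0.5·s(s−1) + (k−s) + ρ(k−s)(k−s−1)
- Induced correlation = s·a / √Var(total)
- Chance of p < 0.05 = Φ(atanh(r)·√27 − 1.960) + Φ(−atanh(r)·√27 − 1.960)

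**Threshold at n = 30.** With t = 2.048 on 28 degrees of freedom, critical r = 2.048/√(28 + 2.048²) = 0.361. For 80% power, r = tanh((1.960 + 0.842)/√27) = 0.49.

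**Symptom score, 21 items.** Example with s = 3, a = 0.5, ρ = 0.3: Var = 3 + 3 + 18 + 0.3·18·17 = 115.8, and r = 1.5/10.76 = 0.139. The table gives the induced r, with the chance of significance in brackets.

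| Overlapping items | a = 0.3, ρ = 0.5 | a = 0.5, ρ = 0.3 | a = 0.7, ρ = 0.1 |
|---|---|---|---|
| 1 | 0.021 (5.1%) | 0.043 (5.6%) | 0.091 (7.6%) |
| 2 | 0.043 (5.6%) | 0.090 (7.5%) | 0.187 (16.6%) |
| 3 | 0.068 (6.4%) | 0.139 (11.3%) | 0.284 (33.0%) |
| 4 | 0.094 (7.8%) | 0.192 (17.2%) | 0.380 (54.8%) |

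Over all 36 combinations of s = 1 to 4, a = 0.3, 0.5, 0.7 and ρ = 0.1, 0.3, 0.5, only one induced correlation (0.380) exceeds 0.361.

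**A second set of assumptions.** Take a 16-item scale (an assumed length), a mean inter-item correlation of 0.1 to 0.3 over all items, and item correlations with sleep summing to 0.5 to 1.0. The SD of the total is √(16 + 240·0.1) = 6.32 to √(16 + 240·0.3) = 9.38. The induced r is 0.5/9.38 = 0.053 to 1.0/6.32 = 0.158, and the chance of significance is 5.9% to 13.2%. If the sum is only 0.2 to 0.3, r is 0.02 to 0.05 and the rate is about 5% to 6%.

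**Mood score, 7 categories.** Assume that a total is formed and Vigor is reverse-scored. The first formulas give r = 0.06 to 0.22 with Fatigue alone overlapping, and 0.14 to 0.44 with Fatigue and Vigor. In the planned regression, mood stands beside sleep as an explanatory variable, so these are correlations between two predictors and not false-positive rates. At the top value the variance inflation is 1/(1 − 0.443²) = 1.24, so standard errors rise by about 12% (√1.24 = 1.11 to 1.12). The larger difficulty is interpretation: fatigue counted as mood is no longer credited to sleep.

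**After removal.** Without the overlapping items, the induced correlation is 0 under this model.

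**The case against.** The strongest reply is that the one correlation spelled out uses actigraphy, an accelerometer record that shares no item with any questionnaire. That stands. A reader might infer that the sleep-symptom correlation is non-zero by construction, and for actigraphy this is wrong: any link between recorded sleep and a sleep-complaint item is empirical and may be weak. The reply does not settle the matter. The overview also measures sleep by self-report, the regression refers to sleep measures without limiting them to actigraphy, and a sleep-complaint item can follow recorded sleep while other symptoms stay unchanged.

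Second, a reader might take it as shown that the RPCSQ, PHQ and BDI-II totals contain sleep and fatigue items. The documents do not reproduce those items. Section 4 lists only form names and version dates, and the use of totals is not stated. What the documents do support is the Background's list of complaints and the ANAM Fatigue category.

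Third, a reader might infer that sleep change is to be correlated with mood totals. No section says so. Personality and Psychodiagnostic Assessment says that sleep and mood measures "will be correlated with other measures of neurocognition and neuroimaging (OBJECTIVE 3"), not with each other. The mood point is therefore confined to the attribution in the regression.

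Fourth, sleep disturbance is a legitimate part of post-concussion severity, and the sleep hypothesis is also tested against performance and imaging measures that have no questionnaire overlap. Both points are fair. They are reasons to keep the standard scores and add an analysis, not to replace those scores.

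**Conclusion.** The concern holds in a limited form. Where symptom or mood scores include sleep or fatigue content, the sleep-symptom association is biased away from zero to the extent that this content follows the sleep measure. The bias is most direct for self-report sleep scales. The separation of sleep from mood is blurred as well, and nothing in the plan guards against either.

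The size is uncertain. The induced correlation is 0.02 to 0.38 for a 21-item symptom score and 0.05 to 0.16 under the second set of assumptions. The chance of a spurious significant result is mostly between 5% and about 20%, and reaches 55% only in the most extreme setting. Every correlation used here is assumed. Overlap alone would seldom reach significance at n = 30, but it would also enlarge an association that is partly real.

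A reader might extend this to the MBLT-SPLT comparison. The documents do not support that: the comparison rests on randomisation and not on the sleep-symptom association. What is at risk is the explanatory claim that better sleep goes with recovery of other symptoms.

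**What to change.** - State which scores (totals or subscores) of each symptom and mood scale enter the sleep-symptom association and the regression under the third outcome.
- Name actigraphy as the main sleep measure for the sleep-symptom association, with the self-report scales as supporting measures.
- List in advance, from the forms themselves, any sleep and fatigue items in the symptom and mood scores. Add an analysis of the association and of the regression with those items removed.
- Claim that better sleep goes with recovery of other symptoms only if the association holds in that analysis.
- Keep the standard scores for the MBLT-SPLT comparison.

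The cost is a few sentences in the analysis section and one additional run of each analysis, provided that item-level responses are kept. The shortened scores are slightly less reliable, so a true association will be estimated with somewhat less precision.
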